If a consumer agrees to consider participating and a research associate is not present at JVS, the JVS professional will ask potential participants if they would like to fill out a contact form and have a Research Associate contact them at a later time. Contact form allows participants to provide phone number for themselves and another contact and an email address, Confidentiality will be emphasized. Research Associates will re-contact potential participants who voluntarily complete contact forms by phone and briefly describe the study. If participants contact research staff via the email provided on the contact form at any time during the study, research staff will respond via email. If the potential participant remains interested, the Research Associate will schedule an in-person meeting at JVS to obtain informed consent. Once informed consent is obtained, the participant will be offered an appointment for a baseline assessment interview. After completion of the baseline assessment interview, those who qualify to participate will be offered participation. .

Participants will be 300 men and women aged 18-60 who are seeking vocational services at JVS (96 JVSD; 204 JVSLA) who meet the inclusion and exclusion criteria below. We expect to be able to recruit enough JVS consumers to fill the groups within 3 to 4 weeks depending on potential participant flow. Our screening efforts have found that approximately 27% of JVS consumers score 5 or greater on the MINI-SPIN. Of those who

score 5 or more, we anticipate that approximately 70% will agree to undergo a formal baseline interview for the pilot study. Of these, we anticipate that approximately 83% will meet full study criteria. Of these, we anticipate that 75% will be randomized. We estimate that we will need to screen 2500 people over our 34-month recruitment interval (JVSD=850; JVSLA= 1650) in order to complete the RCT. Given the large number of new clients entering JVSD and JVSLA services each year, we do not anticipate any difficulty recruiting a *minimum* of 8 participants per month at JVSLA or 6 participants per month at JVSD, but we *expect* to recruit approximately 16 per month at JVSLA and 10 per month at JVSD, resulting in an average of 15 days waiting period or less before randomization.

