Randomization. We will randomize each cohort of six to either WCBT or VAU, until 17 WCBT and 17 VAU groupings are completed at JVSLA and 8 WCBT and 8 VAU groupings are completed at JVSD. In our R34, there was a median wait time of 15 days from assessment to randomization and median wait times were identical for WCBT (2.14 weeks) and VAU (2.14 weeks). We will not reduce group size in response to a longer-than-expected wait. We will re-assess participants on key assessment measures immediately prior to randomization for those who wait beyond one week. In our R34, groups assembled every two to three weeks and the randomization scheme was acceptable (100% of qualified participants agreed to be randomized). Participants will receive \$20 for attending randomization meeting. This reimbursement is for travel and any meals missed during the meeting.

Selection and delivery of the control condition. The proposed study aims to test the effect of WCBT on social anxiety and employment outcomes among unemployed, job seekers with SocAD. A comparison to treatment as usual is considered to be the most appropriate comparison condition for an effectiveness study because evidence-based psychosocial treatments for social anxiety are currently not provided for most unemployed people with social anxiety disorder. Thus, comparison to vocational services as usual (VAU) best tests an effectiveness-based hypothesis that WCBT leads to improved outcomes for work-seeking persons with social anxiety as compared to services as usually delivered in a vocational rehabilitation setting.

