Aim 2. Evaluate whether improvements in social anxiety mediate the effect of WCBT upon employment related behaviors and outcomes. We hypothesize that reductions in social anxiety will lead to more employment related behaviors and greater employment success. In addition, it is hypothesized that specific reductions in social anxiety will better explain the effects of WCBT on employment compared with general improvements in depression and generalized anxiety. Multilevel SEM will assess whether reductions in social anxiety explain WCBT effects on subsequent employment (hours worked, job search activities, job search self-efficacy). This approach provides several advantages that are essential to testing mediation in this design. First, it accounts for nesting of individuals within randomized groups (119); it allows us to focus on change by using centering to disentangle between- and within-person effects (112); it lets us specify temporal order (i.e., change in social anxiety symptoms precedes change in employment related outcomes), and it accommodates latent variables (e.g., hours worked) (119). In addition, multilevel SEM provides ways to formally compare multiple alternative mediation paths (120), which will be essential to testing our hypothesis that reduction in social anxiety will better explain WCBT effects on employment than improvements in depression and generalized anxiety. Mplus software (121) will be used for these analyses due to its flexible estimation capabilities, use of bootstrap algorithms appropriate for testing indirect effects (122), and ability to test and compare specific mediation effects (123). Simulations conducted in MPlus and ProcClin (124) indicate that power can be expected to exceed .8 to detect significance at $p < .05$ an indirect effect in which the two component standardized direct effects a' (WCBT \rightarrow SocAD) and B' (SocAD \rightarrow employment-related outcome) are .20 or above, which is larger than the minimum a' and B' effects observed in the R34 pilot.

Aim 3. Explore moderators of the effects of WCBT, including site, race/ethnicity, education, prior work experience, psychiatric medication status and comorbid depression. Moderation will be tested by adding moderating variables to the MLM regression models testing mental health and employment outcome effects (Aim 1). Because groups are nested within site (16 sites at JVSD and 34 at JVSLA),

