site-level effect differences will be tested as level 3 interactions with condition; assuming overall average WCBT effects on a given outcome are $d=.5$ or above, power is estimated at .8 to detect a between-site effect difference of $d=.4$ or greater. Moderation by time-invariant individual characteristics (race/ethnicity, education, pre-intervention work experience) will be incorporated as cross-level interactions with condition and with condition and time, in order to test moderation of outcome change trajectory as well as level at a specific post-intervention timepoint. Because it is possible for several moderators to vary from assessment to assessment (e.g., psychiatric medication, depression diagnosis), it may be necessary to model their effects as time-varying covariates at level 1, in cross-level interaction with condition, depending on the observed levels of variability. It is not possible to know in advance how individual-level moderating variables will be distributed across the 50 randomized groups; therefore it is difficult to estimate power to test multilevel moderation of WCBT effects, and projections are necessarily tentative (125). However, assuming that a given dichotomous moderator (e.g., comorbid depression diagnosis) is present in at least 30% of the sample and is distributed relatively evenly across the 50 groups, power should exceed .8 to detect an interaction effect (i.e., between-persons difference in WCBT effect) as small as $d=.20$. Because the JVSD site is expected to have minimal variability on race/ethnicity, we plan to test moderation by this variable only among the 36 groups at the JVSLA site. Power to detect differences in WCBT effects among 3 types of participants – Hispanic (anticipated $n=49$), African-American ($n=59$), and White ($n=110$) – is estimated at .8 for interaction effects as small as $d=.30$.

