Participants will be unemployed male and female adults aged 18 to 60 years, evaluated and diagnosed with social anxiety disorder (SocAD). This research is focused specifically on adults in order to determine whether adding WCBT to usual vocational services will yield superior outcomes (social anxiety symptoms and increased employment) compared to vocational services as usual control condition. Participants on medication for psychiatric conditions will be accepted into the study and medications use will be monitored throughout treatment and at each follow-up point. Those who are unwilling or unable to refrain from outside psychotherapy throughout the 4-week active treatment period will be excluded in order to lessen confounding of study treatment effects with outside therapy effects. Given that the focus of this study lies in the treatment of SocAD, participants with substance use dependence within the past month; current use of opiates or freebase cocaine; chronic neurological disorder; mental retardation; schizophrenia, other psychotic symptoms and/or current bipolar I disorder with manic symptoms that would interfere with study participation; current anorexia nervosa; medical conditions contraindicating study treatment (e.g., history of severe head trauma); or prominent suicidal/homicidal ideation with imminent risk will be excluded. These exclusions also will ensure participant safety and allow them to pursue appropriate health care directed at these other conditions.

Participants who have received a prior course of CBT appropriate for social anxiety (at least 8 sessions) will be excluded since they may represent a pre-selected treatment refractory sample that would confound the investigation of the efficacy of WCBT.

Gender and Minority Inclusion. Our screening efforts yielded a sample that was 33% female and 86% African American, 10% White, and 3% Other at JVSD. At JVSLA, administrative data suggests that we will recruit approximately 49% female participants with 35% White, 29% African American, 24% Hispanic, 10% Asian, and 1% Other. Therefore we expect that the overall sample will be mostly made up of minority group members and that men will outnumber women. All eligible and willing men and women will be enrolled regardless of minority status.

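### The race/ethnicity moderation power is stated for 218 participants in 36 JVSLA groups, but JVSLA will have 204 participants in 34 groups, about 180 of them in the three categories

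*Combined protocol and SAP*

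**What the plan says.** The Aim 3 text under Power Analysis and Statistical Strategy restricts the race/ethnicity test to Los Angeles because Detroit is expected to vary little on this variable: "we plan to test moderation by this variable only among the 36 groups at the JVSLA site". It lists the categories as "Hispanic (anticipated $n=49$), African-American ($n=59$), and White ($n=110" and puts power at .8 for interaction effects as small as d=.30.

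Other parts of the document give different counts for the same site:

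- Participants and Recruitment splits the 300 participants as "96 JVSD; 204 JVSLA".
- Randomization assigns whole six-person cohorts to an arm and runs "until 17 WCBT and 17 VAU groupings are completed at JVSLA and 8 WCBT and 8 VAU groupings are completed at JVSD".
- Aim 3 itself, in its passage on site as a moderator, has "16 sites at JVSD and 34 at JVSLA" (the word sites there evidently means groups).
- Section D 1, Gender and Minority Inclusion, expects JVSLA to be "35% White, 29% African American, 24% Hispanic, 10% Asian, and 1% Other".

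**The concern.** Three subgroups of one site cannot hold more people than the site. The power statement is also implausible beside Aim 1, where all 300 participants give power of .7 for a main effect of d=.30. A difference between subgroup effects of that size, within two thirds of the sample, is harder to detect, yet it is credited with .8.

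Ethnic diversity is one of the reasons the protocol gives for choosing JVSLA as the companion site, and this test is confined to JVSLA. A reader who accepts .8 power at d=.30 could take a non-significant interaction as evidence that WCBT works about equally in the three categories. At the power calculated here, a null result would carry almost no information on that question.

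**Working it through.** **Counts**

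- Groups at JVSLA: 17 + 17 = 34, and 34 × 6 = 204, which matches the recruitment split. With 16 at JVSD the total is 50, the number used in Aim 1. Using 36 would give 52.
- Stated categories: 49 + 59 + 110 = 218, which is 14 more than the whole site. It does not fit 36 groups either, since 36 × 6 = 216.
- The plan's JVSLA mix applied to 204:

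| Category | Share | Share × 204 | Stated in Aim 3 |
|---|---|---|---|
| Hispanic | 24% | 49.0 | 49 |
| African American | 29% | 59.2 | 59 |
| White | 35% | 71.4 | 110 |
| Sum of three | 88% | 179.5 | 218 |

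The discrepancy lies entirely in the White category: 110 − 71.4 = 38.6 (110/71.4 = 1.54). For the total it is 218 − 179.5 = 38.5 (218/179.5 = 1.21). Adding the expected White participants at JVSD (10% of 96) gives 71.4 + 9.6 = 81.0, still short of 110.

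**The plan's own power scale (Aim 1)**

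For 300 people in 50 groups of six, take SE = √[(4/300)(1 + 5 × ICC)] and a two-sided 5% t test on 48 df.

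- ICC .01: SE = .1183. Power is .70 at d=.30, .80 at d=.34 and .90 at d=.39, exactly as stated.
- ICC .03: SE = .1238. Power at d=.36 is .81, consistent with the stated .8.

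These figures come out with no reduction in variance from baseline or repeated measures, so Aim 1 expresses d in units of the unreduced SD. Aim 3 adds moderators to the same models. On this scale a main effect of d=.30 in all 204 JVSLA participants has SE = √[(4/204)(1.05)] = .1435 and power of .53 (32 df).

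**Interaction power on that scale**

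With 1:1 allocation inside each category, the difference between two category effects has SE = √(4/n₁ + 4/n₂). Power is Φ(.30/SE − 1.96), and the detectable difference at power .8 is 2.80 × SE. Clustering is left out, which favours the plan slightly.

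| Contrast | SE, stated n | Power | Detectable d | SE, corrected n | Power | Detectable d |
|---|---|---|---|---|---|---|
| Hispanic v African American | .387 | .118 | 1.08 | .387 | .118 | 1.08 |
| Hispanic v White | .344 | .139 | .96 | .371 | .125 | 1.04 |
| African American v White | .323 | .151 | .90 | .352 | .134 | .99 |

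The 2-df interaction test (noncentral F, four patterns with a maximum difference of .30) has power .11 to .15 with the stated sizes and .10 to .13 with the corrected ones.

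**Other readings of the .8**

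- If baseline and repeated measures remove 50% or 75% of the variance (assumed; the documents give no figure), corrected pairwise power is .19 to .23 or .34 to .40. The detectable difference is .70 to .77 or .49 to .54.
- Reaching .8 at d=.30 with the stated sizes needs residual variance of about 8% to 13% of the total.
- Reading .30 as Cohen's f gives .98 with the stated sizes, and f=.15 gives .49. Neither is .8.

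**The case against.** The strongest reply is that two matters are mixed. The count error alone does little: if .8 were right for 49/59/110, cutting White to 71 would lower power to about .69 to .77 and raise the detectable d to about .31 to .34, with no change for Hispanic v African American. The low power is therefore a fault of the method, and the document shows no calculation for this test: no ICC, residual variance, contrast or definition of d. That the .8 was computed on these counts is inferred from their being stated together. The first part stands, and the two faults should be kept apart. The second does not rescue the figure. The Aim 1 numbers reproduce without any variance reduction, and nothing in the document supports residual variance near 10%.

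A second reply is that the mix is approximate. Section D 1 takes it from administrative data, and the opening of Section D describes the second site as serving a mainly Latino population, which sits poorly with 24% Hispanic. That is fair, and the sponsor should confirm the expected mix. It does not alter the conclusion. If all 204 participants fell into two equal categories of 102, SE = 2√(2/102) = .280, and power at d=.30 would be Φ(1.07 − 1.96) = .19.

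Third, Aim 3 is exploratory and its text already calls moderation projections tentative. This limits the consequence. But that caveat concerns how moderators spread across groups; it does not cover category sizes that exceed the site.

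**Conclusion.** The passage is wrong as written in two separate respects.

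The counts are certain from the document alone: 34 groups and 204 people, not 36 and 218. The White figure of about 71 and the three-category total of about 180 rest on the plan's approximate mix.

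The .8 at d=.30 is not supported with either set of sizes. On the Aim 1 scale (two-sided 5%, unreduced SD, equal allocation within category) true power is near .12 to .13, and the detectable pairwise difference is about d=1.0 to 1.1. Under the assumed 75% variance reduction that difference would still be about .5.

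The primary sample size, the randomization and Aim 1 are untouched, so this is a correction that should be made rather than a threat to the trial.

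**What to change.** In the Aim 3 race/ethnicity text:

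1. Change the JVSLA group count to 34.
2. Give the anticipated sizes as Hispanic 49, African American 59 and White 71 (about 180 of 204), after the sponsor confirms the expected mix against the description of the site in the opening of Section D.
3. Replace the claim of .8 power at d=.30 with the detectable difference on the Aim 1 basis, about d=1.0 to 1.1 pairwise. State the contrast, alpha, ICC and residual variance assumed. If a variance reduction is claimed, give its source and show the range.
4. Say that category-specific effects and their differences will be reported with confidence intervals as descriptive, and that a non-significant interaction will not be read as evidence of equal effects.

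The cost is wording and restated figures. Recruitment, randomization, data collection and the models do not change.

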We will use the same MLM approach that we used in our R34 pilot to compare individuals assigned to WCBT vs. VAU. 3-level models will incorporate repeated measures on individuals nested within the 50 6-person groups randomly assigned to WCBT or VAU. HLM software will be used (115). Individual baseline scores on each outcome variable will be incorporated as level 2 covariates to increase the precision and statistical power of tests of the randomized intervention and reduce regression to the mean artifacts (116). Observations will be centered at a post-intervention or follow-up time point to provide a straightforward WCBT vs. VAU comparison on outcome level. Persistence of intervention effects will be assessed through WCBT vs. VAU comparisons on the level 2 slopes characterizing individual outcome trajectories through 52-week follow-up; quadratic or piecewise slope terms (117) will be included if needed to reflect acceleration or slowing of change over time. Power estimates for the planned MLM analyses were conducted using Optimal Design software (118). The entire sample of 300 individuals, nested within 50 groups, with 5 assessments over time, will provide power of .8 to detect (at 2-tailed $p < .05$) an intervention effect on intercept or slope of at least $d=0.34$; power estimates range from .7 to detect $d=.30$ to .9 to detect $d=.39$. Effect sizes in the R34 pilot ranged from .46 for hours worked to 1.36 for social avoidance; this suggests that power in this larger R01 will be adequate to detect condition differences on all outcomes, including employment. These estimates assume a minimum intraclass correlation (ICC) between groups of .01, which is larger than the ICCs observed in the R34 pilot. If the ICC for the R01 is found to be substantially higher at .03, the effect size detectable with power of .8 will rise only slightly, from $d= .34$ to $d=.36$.

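### The stated power of .8 for race/ethnicity interactions of d=.30 is not supported by the plan's own subgroup counts or by its Aim 1 benchmark

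*Combined protocol and SAP*

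**What the plan says.** The power section under Aim 3 restricts the race/ethnicity test to one site: "we plan to test moderation by this variable only among the 36 groups at the JVSLA site". It gives the subgroup sizes as "Hispanic (anticipated $n=49$), African-American ($n=59$), and White ($n=110" and says that power to detect differences in WCBT effect among them "is estimated at .8 for interaction effects as small as $d=.30". No formula, alpha, ICC or R-squared accompanies that figure. Just before it, for another moderator, the same paragraph makes clear what an interaction d means: an "interaction effect (i.e., between-persons difference in WCBT effect) as small as $d=.20".

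Under Aim 1, the full 300 participants in 50 groups give "power of .8 to detect (at 2-tailed $p < .05$) an intervention effect on intercept or slope of at least $d=0.34", and "power estimates range from .7 to detect $d=.30$ to .9 to detect $d=.39". Those figures assume an ICC of .01. Baseline scores are to be covariates, but no variance reduction is stated.

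The Randomization paragraph continues "until 17 WCBT and 17 VAU groupings are completed at JVSLA", which is 34 groups of six, or 204 people. The recruitment section also gives 204 for JVSLA.

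**The concern.** The Aim 3 figure asks for a harder comparison, in fewer people, at a smaller effect, yet claims at least the power that Aim 1 claims. Aim 1 has power .7 at d=.30 for one overall effect in 300 people. Aim 3 claims .8 at d=.30 for a difference between two or more effects in about 218 people. When a sample is split in two, the standard error of the difference between the two treatment effects is about twice that of the overall effect, and more if the split is uneven.

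The opening of the design section justifies the second site partly by its largely Latino clientele, so this moderation result is likely to be read closely. A reader who trusts .8 at d=.30 could take a non-significant interaction as good evidence that WCBT works about equally well in the three groups.

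**Working it through.** **Inputs from the plan.** 50 groups of six, 1:1, two-sided .05, ICC .01 (Aim 1); 36 JVSLA groups and counts 49/59/110, total 218 (Aim 3). **Assumptions.** SD 1; alpha and ICC carry over from Aim 1; arms split evenly within each subgroup; no dropout, which favours the plan.

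**1. Reproduce Aim 1.** SE = sqrt(4 × (.01 + .99/6) / 50) = sqrt(4 × .175 / 50) = .118. The noncentral t with 48 df gives power .700, .804 and .898 at d=.30, .34 and .39. These are the plan's .7, .8 and .9, obtained with no gain from covariates or repeated visits.

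**2. Overall effect in the 36 groups.** SE = sqrt(4 × .175 / 36) = .139. With 34 df, power at d=.30 is .55 and the detectable overall effect is d=.40. So even the overall effect falls short of .8 at d=.30.

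**3. Subgroup differences.** SE = sqrt(4/n1 + 4/n2). Power = Φ(.30/SE − 1.96) plus a negligible opposite tail. Detectable difference = (1.960 + .842) × SE. For White against the other two: sqrt(4/110 + 4/108) = .271; .30/.271 − 1.96 = −.85; power .198; detectable 2.802 × .271 = .76.

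| Contrast | SE | Power at .30 | Detectable d | Power, R² = .5 | R² needed for .8 |
|---|---|---|---|---|---|
| Hispanic vs African-American (49, 59) | .387 | .121 | 1.08 | .195 | .92 |
| Hispanic vs White (49, 110) | .344 | .141 | .96 | .235 | .90 |
| African-American vs White (59, 110) | .323 | .153 | .90 | .260 | .89 |
| White vs other two (110, 108) | .271 | .198 | .76 | .347 | .84 |

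The R² columns multiply SE by sqrt(1 − R²); the R² values are assumptions. A t reference with 212 df lowers the powers by about .003 and raises the largest detectable difference to 1.09. Removing the between-group variance at ICC .01 to .03 raises the best case only from .198 to .203. One-sided testing gives .19 to .30 without adjustment.

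**4. Omnibus test, 2 df.** Noncentrality = Σ (n/4)(δ − weighted mean δ)². If only White participants differ, by .30, the weighted mean is .30 × 110/218 = .151, and the noncentrality is 27.5 × .149² + 27 × .151² = 1.23; power is .15. Over six patterns with a range of .30, power is .10 to .15.

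**5. Repeated visits.** Average the four post-baseline visits, adjust for baseline, and assume equal correlation ρ. The variance factor is (1 + 3ρ)/4 − ρ², which is .385, .375, .285 and .210 at ρ = .3, .5, .7 and .8. Power at d=.30 (t reference) is then .43, .44, .54 and .67 for White vs the other two. For 49 vs 59 it runs from .24 to .39. The best contrast needs a factor of 1 − .844 = .156 to reach .8, which means ρ of about .86.

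**6. Other readings of d.** Taken as an overall effect in 218 people (clustering ignored), power is .60. Taken as Cohen's f=.15 it is .49, and as f=.30 it is .98. None gives .8.

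**7. The counts.** 49 + 59 + 110 = 218 exceeds 204. The Gender and Minority Inclusion paragraph expects 24% Hispanic, 29% African American and 35% White at JVSLA. Of 204 that is 49, 59 and 71, so only the White count disagrees. With 49/59/71 the SEs are .387, .371, .352 and .306, power is .12 to .17, and the detectable difference is about .86 to 1.09.

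**The case against.** The strongest reply is that the figures of .12 to .20 do not describe the planned analysis. The plan specifies three-level longitudinal models with baseline scores as covariates, expressly to gain power, and race/ethnicity is added to those models. This stands. Steps 3 and 5 show that the gain could double or triple the unadjusted power. A reader might therefore wrongly infer from the unadjusted numbers that the planned test has only 10 to 20% power and says almost nothing. The documents give no correlation or R-squared from which to conclude that.

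The gain does not rescue .8, however. It would take an R-squared of about .84 or more, or a visit correlation of about .86 or more. A gain of that size would also bring Aim 1's detectable effect well below the stated .34. The averaging in step 5 also does not apply to a slope interaction or to a test at one time point.

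Second, Aim 3 is framed as exploration, and the text itself calls its moderation projections tentative. That lowers the consequence. But the reason given is that the spread of moderators across groups is unknown, and this cannot turn .2 into .8.

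Third, no sample size, primary analysis or decision rule rests on this sentence, and nothing in the plan says that a null interaction will be reported as equal benefit. A reader might infer that intention, but the documents do not state it. The risk lies in how the .8 could be used later.

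**Conclusion.** The stated power of .8 at d=.30 is not supported. On the unadjusted scale that matches Aim 1, power is about .12 to .20 for the four contrasts and .10 to .15 for the omnibus test, with detectable differences of about d=.76 to 1.09. With gains the plan does not quantify, power rises to about .19 to .35 (R-squared .5) or .24 to .67 (four averaged visits, correlations .3 to .8), still below .8. These results assume an even arm split within subgroups, and alpha and ICC carried over from Aim 1. They take 110 White participants as given, which favours the plan.

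The point is confined to this moderator statement. It does not show that the trial is underpowered for Aim 1, whose figures at ICC .01 reproduce. Nor should the unadjusted 49/59/110 results be printed as the design's true power, because those counts conflict with the rest of the protocol.

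**What to change.** Withdraw the claim of .8 at d=.30. First reconcile the JVSLA numbers: 34 groups and 204 people against 36 groups and 218, and about 71 White participants against 110. Then restate power and the detectable subgroup difference from the reconciled counts, giving the contrast tested, the alpha, the ICC, and any R-squared or repeated-measures gain assumed. If the counts are 49/59/71, the unadjusted values are power of about .12 to .17 at d=.30 and a detectable difference of about d=.86 to 1.09.

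Add a reporting rule: give the WCBT effect with its 95% CI in each subgroup and the 95% CI of each difference, and do not read a non-significant interaction as equal effects.

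The cost is a rewritten power statement and a short reporting rule. No participants, visits or data are added. The stated figure becomes less favourable.
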